7.8.3 Additional Efficacy Endpoint(s)

PAC-QOL Questionnaire:

The PAC-QOL will be analyzed separately for the first 24 items that comprise the Dissatisfaction Index and for the last 4 items that comprise the Satisfaction Subscale at Baseline, and at Weeks 2 and 4. As the PAC-QoL is performed during the visit missing data should only occur when the entire questionnaire is missing, rather than individual items. When the PAC-QoL is missing then LOCF will be used to carry forward the nearest previous value.

The Dissatisfaction Index will be analyzed using van Elteren's test stratified by center to examine the difference between lubiprostone and placebo. Additionally the endpoint will be

CROSS-REGIONAL TEMPLATE

Template Number:	C-TMPL-DO-801	Page:	22 of 28
Version Number:	1.2	Effective Date:	14 Sep 2015
This version replaces:	1.1		
Parent Document:	C-SOP-DO-800		
Template Title:	Statistical Analysis Plan (Legacy Takeda)		

analyzed using ANOVA models with center and treatment in the model as a sensitivity analysis. The estimated LS means, related mean difference and associated 95% CI will also be presented to aid interpretation of the clinical effect.

The Satisfaction Index will be categorized by combined scores of the 4 items as either poor (0-4), fairly good (5-8), good (9-12), or excellent (13-16) and will be analyzed by van Elteren tests, stratified by center, at Baseline, and at Weeks 2 and 4 separately. Additionally a cumulative logistic regression model will be used with treatment and center as factors as a sensitivity analysis. The estimated odds ratio and associated 95% CIs will also be presented to aid interpretation of the clinical effect.

CCI

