9.1.8 Additional Endpoints

9.1.8.1 Quality of Life Evaluation

The PAC-QOL is a health related QOL instrument designed specifically to evaluate an adult subject's assessment of constipation over time. It is self -administered assessment consisting of

28 items and is designed to cover the 2 weeks prior to the questionnaire being completed. Each item is scored from 0 to 4; a lower score is better. The 28 items are grouped into 4 subscales: physical discomfort, psychosocial discomfort, worries and concerns, and satisfaction.

The PAC-QOL will be assessed at Day -1 (prior to the start of study drug), mid-way through the Double-Blind Treatment Period on Day 15, and at the end of the Double-Blind Treatment Period, on Day 29.

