6.0 DETERMINATION OF SAMPLE SIZE

Assuming equal allocation, a power of 90%, an alpha level of 0.05 for a 2-sided test, a placebo mean of 4, a treatment mean of 5.9 and a common standard deviation of 4 for SBM frequency at Week 1 and using the Wilcoxon-Mann-Whitney test [1], a total sample size of 198 is required. The Wilcoxon-Mann-Whitney test is a non-parametric test of the null hypothesis that the distribution is the same for both placebo and treatment responses against the alternative that there is a location difference between the two. The primary analysis will be conducted using the van Elteren test, which is a stratified version of the Wilcoxon-Mann-Whitney test; use of the Wilcoxon-Mann-Whitney test for sample size estimation will provide an approximate sample size for the van Elteren analysis. The estimates of placebo and treatment response are based on a previous study conducted by Sucampo Pharmaceuticals in the United States of America (Protocol No. SPI/0211SC0232).

The primary endpoint requires subjects to complete at least 4 days of the study diary, therefore assuming a non-evaluable rate of 3% by Day 4 an additional 6 subjects are required, giving a total of 204 subjects.

CROSS-REGIONAL TEMPLATE

Template Number:	C-TMPL-DO-801	Page:	9 of 28
Version Number:	1.2	Effective Date:	14 Sep 2015
This version replaces:	1.1		
Parent Document:	C-SOP-DO-800		
Template Title:	Statistical Analysis Plan (Legacy Takeda)		

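### Banding the 0-16 PAC-QOL Satisfaction sum into four classes before the van Elteren test is valid but gives away some power on this additional endpoint

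*SAP*

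**What the plan says.** Protocol 9.1.8.1 gives the item scoring for the PAC-QOL: "Each item is scored from 0 to 4; a lower score is better". Four items therefore give a sum from 0 to 16, which has 17 levels.

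SAP 7.8.3 reduces that sum to four classes: "The Satisfaction Index will be categorized by combined scores of the 4 items as either poor (0-4), fairly good (5-8"), followed by 9-12, labelled good, and 13-16, labelled excellent. The classes "will be analyzed by van Elteren tests, stratified by center, at Baseline, and at Weeks 2 and 4 separately". A second model follows on the same classes: "Additionally a cumulative logistic regression model will be used with treatment and center as factors as a sensitivity analysis". Protocol 13.1.3.3 has the same cut points and the same methods, so the SAP did not introduce the rule. Neither document explains the cut points, and the visible text plans no test of the ungrouped sum.

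The other part of the questionnaire is handled differently in the same SAP section: "The Dissatisfaction Index will be analyzed using van Elteren's test stratified by center", with no categories stated.

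The PAC-QOL is listed as an additional endpoint in protocol 5.2.3 and SAP 5.0. No power, effect size or SD is stated for it.

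**The concern.** Banding makes a rank test treat unequal outcomes as equal and some near-equal outcomes as different. Subjects scoring 5 and 8 are tied, while a subject scoring 4 is ranked below one scoring 5 exactly as below one scoring 8. The van Elteren test needs only ordered data and deals with ties through midranks, so nothing in the method calls for the grouping. Banding the Satisfaction sum but, as far as the text shows, not the Dissatisfaction Index is unexplained.

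What is at stake is the sensitivity of the satisfaction comparisons. A real difference that falls mostly within bands would show only weakly.

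**Working it through.** **1. The plan's own sample-size figure.** SAP 6.0 states "Assuming equal allocation, a power of 90%, an alpha level of 0.05 for a 2-sided test" and "a placebo mean of 4, a treatment mean of 5.9 and a common standard deviation of 4" for Week 1 SBM frequency, with a total of 198. The two-sample t-test for a difference of 1.9 and SD 4 needs 94.11 per arm. Dividing by the Wilcoxon efficiency 3/π gives 98.55, so 99 per arm and 198 in total, as stated. The 3% allowance gives 198 × 1.03 = 203.9, so 204, or 102 per arm. (Dividing instead, 198/0.97 = 204.1, would round up to 205; this has no bearing here.) The figure concerns the primary endpoint only. All that carries over is 102 per arm, which assumes that every randomized subject contributes a score.

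**2. Assumptions for the satisfaction score.** The documents supply the 17 levels and the cut points, which give bands of 5, 4, 4 and 4 levels. The rest is assumed: a normal score rounded and clipped to 0-16, placebo mean 4, 6 or 8, SD 3, 4 or 5, and a treatment shift of 2 points up or down.

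**3. Formulas.** Let θ be the probability that a treated subject scores above a placebo subject, with ties counted as one half, and let p be the level probabilities averaged over the two arms.

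- Noncentrality per unit: λ = 12(θ − 0.5)² / (1 − Σp³)
- Power: Φ(√(102λ/2) − 1.96)
- Relative efficiency of the bands: λ(bands) / λ(full sum)

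**4. One case in full: mean 6, SD 4, shift +2.**

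- Full sum: θ − 0.5 = 0.1373 and 1 − Σp³ = 0.9944, so λ = 0.2276. Power is Φ(3.41 − 1.96) = 92.6%.
- Bands: θ − 0.5 = 0.1250 and 1 − Σp³ = 0.9096, so λ = 0.2061. Power is Φ(3.24 − 1.96) = 90.0%.
- Efficiency: 0.2061/0.2276 = 0.905.

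**5. All cases (efficiency; power on full sum → on bands, %).**

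| Placebo mean, SD | Shift +2 | Shift −2 |
|---|---|---|
| 4, 3 | 0.826; 99.4 → 98.2 | 0.675; 99.3 → 95.2 |
| 4, 4 | 0.845; 92.4 → 87.6 | 0.737; 91.5 → 81.7 |
| 4, 5 | 0.857; 77.6 → 71.2 | 0.780; 76.0 → 65.3 |
| 6, 3 | 0.883; 99.4 → 98.7 | 0.826; 99.4 → 98.2 |
| 6, 4 | 0.905; 92.6 → 90.0 | 0.845; 92.4 → 87.6 |
| 6, 5 | 0.906; 78.3 → 74.2 | 0.857; 77.6 → 71.2 |
| 8, 3 | 0.888; 99.4 → 98.8 | 0.883; 99.4 → 98.7 |
| 8, 4 | 0.918; 92.6 → 90.4 | 0.905; 92.6 → 90.0 |
| 8, 5 | 0.919; 78.3 → 74.8 | 0.906; 78.3 → 74.2 |

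An upward shift costs about 1 to 6 points of power, and a downward shift about 1 to 11. No case favors the bands.

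**6. Check with the stratified test.** The van Elteren test was simulated with 10 equal centers and 4,000 runs per case. Power on the full sum against the bands was 77.0% and 74.5% (mean 8, SD 4, shift 1.6), 76.9% and 72.1% (mean 6, SD 3, shift 1.2), and 77.3% and 67.8% (mean 4, SD 3, shift 1.2). With no shift, the rejection rate was 4.6% and 4.5% (mean 8, SD 4), and 4.9% and 4.9% (mean 6.5, SD 2).

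**7. Wider assumptions.** With placebo mean 2 to 14, SD 2 to 5, and an upward shift chosen to give 80% power on the full sum, efficiency runs from 0.46 to 0.92 and power on the bands from 48% to 77%. The low end arises when scores pile up near one end of the scale.

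**The case against.** The strongest reply is that nothing here is an error. The banded rule is prespecified, identical in both documents and controls type I error. The endpoint is neither primary nor secondary, no power is claimed for it, and no multiplicity scheme depends on it. Named classes are easy to read, and at present the p-value and the odds ratio describe the same variable. All of this stands, and it makes the point a cheap improvement and no more.

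A reader might infer more than the documents support, in four ways:

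- **That a fixed number of subjects is wasted.** Efficiency of 0.92 to 0.68 could be turned into 204 × 0.08 = 16 to 204 × 0.32 = 65 subjects. The arithmetic follows, but it rests wholly on assumed distributions and suggests more harm than the power figures show: the lowest efficiency in the table goes with power of 99.3% falling only to 95.2%.
- **That the loss is severe.** The 0.46 in the wider range needs scores crowded at an end of the scale, which the documents neither show nor rule out.
- **That the reported effect would become more precise.** SAP 7.8.3 plans no van Elteren confidence interval for Satisfaction, unlike 7.8.1 and several endpoints in 7.8.2. The only interval is for the cumulative odds ratio, which stays on the bands.
- **That the change has no downside.** It departs from the protocol, and the p-value and the odds ratio would then rest on different codings and could disagree.

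Redacted text follows the Satisfaction paragraph in SAP 7.8.3, so an ungrouped analysis there cannot be excluded. Protocol 13.1.3.3 shows no redaction between that paragraph and the safety text, and plans none.

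**Conclusion.** The point holds as a minor matter of efficiency. Grouping 17 ordered levels into four discards information that the chosen test can use, with no gain in error control. Under the stated assumptions the bands keep about 0.68 to 0.92 of the efficiency and cost about 1 to 11 points of power. These figures illustrate the loss and are not estimates for this trial.

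The size also depends on an unresolved matter in the same rule. Protocol 9.1.8.1 says that lower item scores are better, yet the class for sums of 13-16 carries the most favorable label. The documents do not settle whether improvement moves the sum up or down, and hence which column of the table applies. The two-sided p-value is unaffected, but the class labels and the reading of the odds ratio are not.

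**What to change.** Before unblinding, amend SAP 7.8.3 so that the van Elteren test for Satisfaction uses the ungrouped 0-16 sum at all three planned time points: Baseline, Week 2 and Week 4. Keep the four classes for the descriptive table and the cumulative logistic model. Record the departure from protocol 13.1.3.3 and its reason in SAP 7.13; SAP 7.1 already requires reasons for departures to be documented.

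In the same revision, reconcile the scoring direction in protocol 9.1.8.1 with the class labels, and state which direction of the odds ratio favors lubiprostone.

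The cost is a short SAP revision using data already collected. Add a sentence telling readers that the p-value refers to the full sum and the odds ratio to the four classes.

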13.1.3.3 Additional Endpoints

Efficacy

PAC-QOL Questionnaire: The PAC-QOL will be analyzed separately for the first 24 items that comprise the Dissatisfaction Index and for the last 4 items that comprise the Satisfaction Subscale at Baseline, and at Weeks 2 and 4.

The Dissatisfaction Index will be analyzed using van Elteren's test stratified by center to examine the difference between lubiprostone and placebo. Additionally the endpoint will be analyzed using ANOVA models with center and treatment in the model as a sensitivity analysis. The estimated LS means, related mean difference and associated 95% CI will also be presented to aid interpretation of the clinical effect.

The Satisfaction Index will be categorized by combined scores of the 4 items as either poor (0-4), fairly good (5-8), good (9-12), or excellent (13-16) and will be analyzed by van Elteren tests, stratified by center, at Baseline, and at Weeks 2 and 4. separately. Additionally a cumulative logistic regression model will be used with treatment and center as factors as a sensitivity analysis. The estimated odds ratio and associated 95% CIs will also be presented to aid interpretation of the clinical effect.

Safety

Adverse events will be summarized using the safety analysis set. No statistical testing or inferential statistics will be generated.

All AEs will be coded using the MedDRA. Data will be summarized using preferred terms (PTs) and primary system organ class (SOC).

Vital signs, clinical laboratory values, and body weight will be summarized by treatment group for both actual and change from baseline values.

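### PAC-QOL is significance-tested between arms before treatment, while no inferential comparison at Weeks 2 and 4 adjusts for the Day -1 score already collected

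*SAP*

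**What the plan says.** Protocol 9.1.8.1 sets the timing: "The PAC-QOL will be assessed at Day -1 (prior to the start of study drug"), then Day 15 and Day 29. The SAP labels the last two Week 2 and Week 4.

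SAP 7.8.3 splits the questionnaire into a 24-item Dissatisfaction Index and a 4-item satisfaction score grouped into four categories. Its lead sentence has the first 24 items analyzed separately, and likewise calls for analysis "for the last 4 items that comprise the Satisfaction Subscale at Baseline, and at Weeks 2 and 4".

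- **Satisfaction Index.** The test at Baseline is explicit. The SAP says the index "will be analyzed by van Elteren tests, stratified by center, at Baseline, and at Weeks 2 and 4 separately", and protocol 13.1.3.3 says it "will be analyzed by van Elteren tests, stratified by center, at Baseline, and at Weeks 2 and 4". In addition, "a cumulative logistic regression model will be used with treatment and center as factors as a sensitivity analysis".
- **Dissatisfaction Index.** "The Dissatisfaction Index will be analyzed using van Elteren's test stratified by center to examine the difference between lubiprostone and placebo". This sentence names no time point. The index is also "analyzed using ANOVA models with center and treatment in the model as a sensitivity analysis", and the protocol gives the same model terms: "using ANOVA models with center and treatment in the model as a sensitivity analysis".

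Baseline is used elsewhere in two ways. SAP 7.8 and protocol 13.1.3 call for descriptive change-from-baseline summaries by treatment and visit. Under the carry-forward rule in SAP 7.8.3, a missing Week 2 questionnaire takes the nearest earlier value, which is Day -1. ANCOVA stands in the SAP's abbreviation list, but no analysis in the SAP uses it.

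**The concern.** In a properly randomized trial the null hypothesis of a Day -1 comparison is true by design. The test can only return a chance result. SAP 7.1 labels any p-value at or below 0.05 as significant, and nothing in the plan says what follows if a baseline comparison earns that label. The plan would flag an imbalance without any inferential analysis that could account for it.

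Chance differences of this kind do occur in this program. Protocol Table 4.a lists baseline SBM of 1.52 and 1.28 in Study SC0232, with p = 0.012. That is a different endpoint and says nothing about PAC-QOL itself, but it shows how such a p-value can appear and invite questions.

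Meanwhile the Day -1 score could be used to sharpen the Week 2 and Week 4 comparisons and is left out of them. At stake are the width of the PAC-QOL confidence intervals and how far an unlucky allocation colors the PAC-QOL result.

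**Working it through.** **The plan's own figure.** The documents give no power, effect size or correlation for PAC-QOL. The only sizing figure, 198 subjects raised to 204, belongs to Week 1 SBM frequency. It reproduces approximately:

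- Normal approximation, with 1.960 and 1.282 the normal quantiles for 2-sided 5% and 90% power: 2 × (1.960 + 1.282)² × 4² / 1.9² = 93.1 per arm.
- Divided by the Wilcoxon efficiency 3/π: 97.5, so 98 per arm, or 196 in total.
- Starting from the t-test size of 95 per arm: 95 × π/3 = 99.5, so 100 per arm, or 200 in total.

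The stated 198 lies between these, and nothing below changes it.

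**Baseline tests.** Each has a 5% chance of a false finding. For two tests the chance of at least one is 1 − 0.95² = 9.75% if they are independent. It is lower if the two indices are positively correlated, as they may be within the same subjects.

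**Precision at Weeks 2 and 4 (Dissatisfaction Index ANOVA).** Let r be the within-center correlation between the Day -1 score and the follow-up score. It must be taken within center because center is already in the model. The documents give no value, so r = 0.3 to 0.6 is an assumption.

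- Variance of the treatment difference without baseline: 2σ²/n.
- With baseline as a linear covariate: 2σ²(1 − r²)/n.
- Ratio of variances: 1 − r². Ratio of interval widths: √(1 − r²).
- Unadjusted sample size of equal precision: 204/(1 − r²).

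| r | variance ratio | interval width ratio | equivalent total N | power if unadjusted power is 80% |
|---|---|---|---|---|
| 0.3 | 0.91 | 0.95 | 224 | 84% |
| 0.5 | 0.75 | 0.87 | 272 | 90% |
| 0.6 | 0.64 | 0.80 | 319 | 94% |

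The cut in residual variance is therefore 9% to 36%, equivalent to 10% to 56% more subjects (1/0.91 = 1.10; 1/0.64 = 1.56).

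**Chance imbalance.** In an unadjusted follow-up comparison, a standardized baseline difference z_b shifts the expected follow-up statistic by r × z_b. Given z_b, that statistic is approximately normal with mean r × z_b and standard deviation √(1 − r²) under no treatment effect. At z_b = 1.96 the chance of exceeding ±1.96 is:

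- r = 0.3: 7.9%
- r = 0.5: 12.9%
- r = 0.6: the upper limit is (1.96 − 1.176)/0.8 = 0.98, giving 16.4%

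With perfectly balanced arms (z_b = 0) the same chance is below 5%. At r = 0.5 the limit is 1.96/0.866 = 2.26, giving 2.4%. Averaged over all possible allocations it is 5%.

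**Scope.** These formulas suit a roughly continuous score. In a cumulative logit model a covariate does not reduce a residual variance. It changes the odds ratio from marginal to conditional and need not narrow its interval. The table should not be read across to the Satisfaction Index.

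**The case against.** The best defense is that nothing here is invalid and little depends on it. Treatment is randomized, so the unadjusted Week 2 and Week 4 comparisons are unbiased and hold their nominal error rate. PAC-QOL is an additional endpoint, with no power or success claim attached. No rule uses a baseline p-value to choose covariates, exclude subjects or alter an analysis. Stratifying by center alone is the plan's uniform choice, including for the primary endpoint, and protocol and SAP agree on it. All of this stands, and it limits the weight of the point. It does not give the baseline test a purpose or explain why a measured covariate is left out.

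A reader might infer more than the documents support:

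- **That the Week 2 and Week 4 results are biased or their error rate inflated.** The raised rates above are conditional on one unlucky allocation.
- **That an imbalance passes in full into follow-up.** It carries through in proportion to r, so about 30% to 60% of the standardized difference over the assumed range.
- **That baseline is ignored altogether.** It is summarized descriptively and can enter through carry-forward. The gap is in the inferential comparisons.
- **That both indices are expressly tested at Baseline.** Only the Satisfaction Index is. For the Dissatisfaction Index this follows from the lead sentence.
- **That Day -1 is known to be the best predictor.** The documents contain no evidence on this.

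**Conclusion.** The point holds as a low-severity improvement. The between-arm test of the Satisfaction Index at Baseline is uninformative and feeds no decision, and the plan implies the same for the Dissatisfaction Index. The Week 2 and Week 4 comparisons are valid but less precise than the collected data may allow, and they are exposed to realized imbalance.

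The gain of 9% to 36% in residual variance rests on the assumed r and on a roughly linear relation within center, and it applies to the Dissatisfaction Index ANOVA only. If r were near zero, almost nothing would be gained, and one degree of freedom would be lost.

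**What to change.** Settle the following in SAP 7.8.3 before unblinding, so that adjustment is not chosen after seeing a baseline p-value:

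1. Replace the Baseline tests of both indices with descriptive summaries by arm.
2. Add the Day -1 Dissatisfaction Index as a covariate to the Week 2 and Week 4 ANOVA, making it an ANCOVA.
3. Add the Day -1 satisfaction score or category to the cumulative logit model, and state that the odds ratio is then conditional on baseline.
4. Give a simple rule for a missing Day -1 score, for example substituting the mean over both arms, so that no FAS subject drops out of the models.
5. Keep the center-stratified van Elteren tests at Weeks 2 and 4. A center-stratified rank ANCOVA could be added as an optional supplement.

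A Week 2 value carried forward from Day -1 would equal its own covariate. The supportive analysis without imputation in protocol 13.1.3 would show whether that matters.

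The cost is SAP text, one covariate in each of two models and the missing-score rule. Protocol 13.1.3.3 prescribes the unadjusted analysis, so the departure should also be recorded in SAP 7.13. No visit, form, data item or change in sample size is needed.

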7.9 PHARMACOKINETIC/PHARMACODYNAMIC ANALYSIS

Not applicable.

7.10 OTHER OUTCOMES

Not applicable.

7.11 SAFETY ANALYSIS

Safety analyses include AEs, clinical laboratory values, vital signs, and other safety parameters. All safety summaries will be based on the SAF. The analysis of safety data will be restricted to descriptive statistics only unless otherwise specified.

7.11.1 Adverse Events

A pretreatment event (PTE) is defined as any untoward medical occurrence in a clinical investigation subject who has signed informed consent to participate in a study but prior to administration of any study medication; it does not necessarily have to have a causal relationship with study participation.

An AE is defined as any untoward medical occurrence in a clinical investigation subject administered a drug; it does not necessarily have to have a causal relationship with this treatment.

An AE can therefore be any unfavorable and unintended sign (eg, a clinically significant abnormal laboratory finding), symptom, or disease temporally associated with the use of a drug whether or not it is considered related to the drug. AEs are captured from when informed consent has been given until last follow-up visit.

CROSS-REGIONAL TEMPLATE

Template Number: C-TMPL-DO-801

Page: 23 of 28

Version Number: 1.2

Effective Date: 14 Sep 2015

This version replaces: 1.1

Parent Document: C-SOP-DO-800

Template Title: Statistical Analysis Plan (Legacy Takeda)

Treatment-emergent adverse events (TEAEs) will be defined as any AE that occurs after the first dose of study drug and up to the last dose or early termination plus applicable follow up (two weeks). An AE with a completely or partially missing onset date will be counted as a TEAE, unless the partial date information available clearly indicates that the event happened out of the treatment period (e.g. a stop date earlier than the date of first dose). Only TEAEs will be included in summary tables.

There are no AEs of special interest defined for the study.

The MedDRA dictionary, current version, will be used to code all AEs reported during the trial by SOC and PT.

All TEAE summaries will be arranged in alphabetical order of SOC then by descending frequency (subject frequency) of the preferred term (PT) within the lubiprostone treatment group.

AEs with missing intensity will be listed as such in the AE listings, however, will be summarized as severe in summary tables. If the relationship of an event is missing, the relationship for the event will be considered to have been related. In the cases where a subject has multiple AEs with the same SOC or PT the AE with the maximum intensity or strongest relationship will be summarized. When calculating the frequency and percentage of subjects who reported TEAEs, a subject will be counted only once for each SOC or PT when multiple TEAEs are coded to the same SOC or preferred term. Thus, if a subject has two distinct AEs, each of which corresponds to a distinct preferred term but both of which correspond to the same SOC, then that subject will be counted once at that SOC subject-count summary level and once at each of the two preferred-term subject-count summary levels.

The number and percentage of subjects with TEAEs will be summarized in several different tables:

- Overview of TEAEs (including number and percentage of patients and number of events)
- All TEAEs by SOC and PT.
- All TEAEs by SOC.
- All TEAEs by PT.
- Most frequent TEAEs by PT (occurring in $\geq 5\%$ of subjects within one treatment group).
- Most frequent non-serious TEAEs by PT (occurring in $\geq 5\%$ of subjects within one treatment group).
- Relationship of TEAEs to Study Drug by SOC and PT (not related, related).
- Drug-Related TEAEs by SOC and PT
- Intensity of TEAEs by SOC and PT
- Intensity of Drug-Related TEAEs by SOC and PT
- TEAEs Leading to Study Drug Discontinuation by SOC and PT

CROSS-REGIONAL TEMPLATE

Template Number:	C-TMPL-DO-801	Page:	24 of 28
Version Number:	1.2	Effective Date:	14 Sep 2015
This version replaces:	1.1		
Parent Document:	C-SOP-DO-800		
Template Title:	Statistical Analysis Plan (Legacy Takeda)		

- Serious TEAEs by SOC and PT
- Pretreatment Events by SOC and PT
- Pretreatment Serious Events by SOC and PT
- Listing of Deaths, Other Serious Adverse Events, and Certain Other Significant Adverse Events

Subject mappings will also be produced for:

- TEAEs
- TEAEs leading to study drug discontinuation
- Serious TEAEs

A list of PTEs by subject number and MedDRA coding will be presented separately. PTEs will be summarized by SOC and PT.

